9.8 Qualitative methods and data outcomes

Patients eligible for inclusion in the prospective cohort study will also be asked on the consent form if they would be happy to be contacted by a trained member of the MOSES team to be interviewed about the following topics:

- Their views on the patient pathway to date.
- Their views on TBM.
- Their views on CUP in H&N and the psychological impact of not knowing the origin has been identified.
- Their views on the potential diagnostic improvements brought by SSS
- Their views on the possible escalation of treatment brought about by identification and incomplete removal of a primary
- Their views on robotic surgery in general

There is a separate patient information sheet and informed consent form for this qualitative component. Patients not consenting to be contacted regarding the above interviews will not be precluded from participation in the remainder of the study.

After appropriate training in qualitative research methodology, a core committee will meet to agree a final methodology, form a provisional topics list and suggest interview questions. We will then engage with a PPI group to assess topic lists and questions and to hold practice interviews with appropriate feedback. Patients will be recruited for one-to-one interviews at various stages of their treatment.

The interviews will be recorded, and a transcription of the conversation made. The transcription will be reviewed and coded using appropriate software. There will be interval thematic analysis and further recruitment/interviews until saturation (as per Francis method) before final thematic analysis [8]. No patient identifiable data will be recorded as per the methods above. Basic treatment information will be recorded alongside demographics to give context to the answers.

Following the COVID-19 pandemic, it was clarified with the sponsor that remote consent and conduct of qualitative interviews would be acceptable for appropriately informed and consenting patients.

10 Assessment timings

10.1 Summary tables

The following tables summarises the time points at which respective data fields will be gathered and returned:

Procedure		Screening/ Day 0	3 wks.	6 wks.	3 mos.	6 mos.	12 mos.	24 mos.	36 mos.	48 mos.	60 mos.
Local team	Eligibility	x									
	Informed Consent	x									
	Medical and surgical history	x									
	Investigation results	x									
	Conventional histology result		x								
	CRF Completion	Page 1-2	Pages 3, 4, 5				Page 6	ICF v3.0 and above			
Patient/ Local team	Pain questionnaire	x	x	x	x	x	x	ICF v3.0 and above			
	MDADI questionnaire	x	x	x	x	x	x	ICF v3.0 and above			

Return of data		Screening/ Day 0	3 wks.	6 wks.	3 mos.	6 mos.	12 mos.	24 mos.	36 mos.	48 mos.	60 mos.
Local team to return CRF to RMH		x	x				x	ICF v3.0 and above			
Local team to return questionnaires to RMH		x	x	x	x	x	x	ICF v3.0 and above			
Local team obtain germline DNA samples (buccal swabs and/or blood samples)		Any time point									

in person or posted to patient	
Local team return tissues to RMH (TBM +/- tonsil specimens, cervical nodal specimens and buccal swab and/or blood samples)	Any time point

10.2 Pragmatic interpretation of timepoints

The timepoints above are intended to collect data at the following points in the patients care:

- Baseline Prior to TBM surgery
- 3 weeks Following TBM surgery
- 6 weeks Just prior to starting radiotherapy (if applicable)
- 3 months Just after completing radiotherapy (if applicable)
- 6 months -
- 12 months -

11 Data management

The study will require a database to store pseudonymised data. Patient data will be collected on a paper case report form (CRF) at each site. The CRF will contain no patient identifiable data and will be pseudonymised with a study ID. The CRFs will be sent to the MOSES team at RMH. This will be entered onto an excel spreadsheet held on an NHS trust computer at the sponsoring organisation, the Royal Marsden Hospital NHS Foundation Trust.

All patient identifiable data will remain at the local site subject to normal data governance practices. None will be sent to or handled by the project management team, except for those consenting to the qualitative study who agree to share their name and contact details on the main study ICF.

12 Statistics and data analysis

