8.3 Exclusion criteria

- Primary site identified by any means prior to being indicated for TBM
- Patients undergoing targeted biopsies or resections
- Patients known to have a history of previous H&N cancers
- Patients known to have undergone previous radiation to the H&N region

9 Study procedure and methodology

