9.2 Consent

Once identified, eligible patients may be approached by the usual care team or research nurse either remotely or in person. No additional outpatient appointments or patient contacts should be required. Patients will be provided with copies of the **Patient Information Sheets (PIS)** and **Informed Consent Forms (ICF)**. Appropriate time will be given to patients to read and digest the information. Written consent will be taken by an appropriately trained member of the clinical team or a research nurse.

Re-consent

Following the implementation of protocol v4.1, patients who had already consented using ICFs prior to v3.0 may be re-approached, by an appropriately trained member of the local team, to re-consent to the study to be able to participate in the extended follow-up and molecular analyses.

Qualitative interviews

For the Qualitative Interviews, consent may be completed remotely by the patient and the MOSES team. As with face-to-face consent, the Patient Information Sheet should be provided, and the patient given adequate opportunity to ask questions about participation in the study. An electronic copy of the consent form will be stored in the Trial Master File by the Sponsor.

9.3 Functional outcomes and pain scores.

Patient will be asked to complete 10 sets of questionnaires: at baseline (pre-operatively); and post-operatively at 3 weeks, 6 weeks, 3 months, 6 months, 12 months, 24 months, 36 months, 48 months and 60 months. Patients will be asked to record their pain score at its worst, at its least and most of the time, on a Numeric Rating Scale. They will be asked to assess their swallow function by completing a M. D. Anderson Dysphagia Inventory (MDADI). Questionnaires may be completed in person, via post or

remotely (including telephone, video-call or electronic form) and returned to the MOSES team on the contact email provided.

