9.7 Handling of tissue specimens and histological processing

All tissue will undergo conventional histological processing at the local site and will be used to influence patient management by the local team according to local practices. The following tissues will then be requested to be sent by the local teams to RMH for further analysis:

- Oropharyngeal tissues from diagnostic surgeries attempting to identify the primary site (i.e., TBM specimens, and tonsils, if available)
- Cervical nodal specimens, from the diagnostic neck biopsies (fine needle aspiration cytology and/or core biopsies) and/or therapeutic neck surgeries, if available
- A buccal swab and/or blood sample (for germline DNA)

Where SSS is indicated (TBM and tonsil specimens, if available) the MOSES team will then send these tissues onto the RVI. Appropriate tissue handling practices will be observed. RMH uses FreezerPro Laboratory Management Software to facilitate handling and tracking of tissue specimens.

Anonymised histopathology reports will be requested from local centres. The macroscopic description will be used to orientate the submitted tissue blocks undergoing step serial sectioning.

Step serial sectioning

The paraffin blocks supplied from TBM and tonsil specimens will undergo step serial sectioning using the following method:

- Steps every 0.5mm with five serial 4 μ m sections taken.
- Each block will be processed in this way until the material is consumed.
- Slides will be stained with haematoxylin and eosin stain (H&E) and examined for signs of SCC.
- If an SCC is identified, then serial sections 2 and 4 will be submitted for HPV testing (p16 immunohistochemistry and high-risk HPV DNA in situ hybridisation).
- Serial sections 1 and 5 will be retained for repeat tests if required.
- The pathologist will compose a report and complete the relevant sections of the CRF.
- Unused material will be returned to the contributing centres if desired. Some material may be retained for further study, as detailed in the PIS and ICF.

Exploratory molecular analysis

Patients will be asked to provide buccal swabs and/or blood samples for germline DNA analysis. These samples may be provided at any time point following recruitment.

Packaging and sending

All MOSES blood and/or buccal swab samples should be collected, labelled, stored and shipped as detailed in the **MOSES Sample Collection Manual**.

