12.2 Study endpoints

For the Primary objective:

- Identification of cancer in the tonsillectomy or TBM specimen on histology.

For the Secondary objectives:

- To compare the pick-up rate of primary cancers in TBM specimens between surgical methods (robotic vs laser vs endoscopic).
 - Identification of cancer in the tonsillectomy or TBM specimen on histology.
 - We anticipate no significant disparity in pick up rate between methods with the limited number of cases in this study.
- To prospectively evaluate swallowing function and pain scores after TBM.
 - We anticipate no significant change in means from pain and MDADI scores between 0 and 6 week questionnaires. Results at 3 weeks are anticipated to be different as still recovering from surgery. Results up to 60 months will evaluate effects of any subsequent treatments and future recovery.
- To understand patient views and experiences of undergoing TBM for suspected HNSCCUP.
 - Qualitative thematic analysis therefore no quantitative end point.
- To report time-to-event data for local, regional and distant disease recurrence, and mortality.
 - Primary emergence rate of around 3% per year.
- To assess the molecular makeup of patients with suspected HNSCCUP undergoing TBM.
 - (Exploratory analysis)

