12.4 Analysis methods

Descriptive analysis only is anticipated. The rate of CH and SSS pick up will be reported in the overall specimens and separately in the sub-group of surgical methods with 95% confidence intervals. The pain scores and swallow recovery with MDADI scores will be reported using mean/median and standard deviation or range as appropriate at each time point of 0, 3 weeks, 6 weeks, 3 months, 6 months and 12 months, 24 months, 36 months, 48 months and 60 months. Similarly, score change between time points will be summarized in the same way. The primary and secondary analysis will be done when the complete sample size is recruited and last patient on the study completed all follow-ups.

Molecular data analysis

Detailed description of the molecular analysis methodology is beyond the scope of this protocol.

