12.8 Expected Outcomes of the Study

TBM is a relatively new surgical procedure with little data relating to patients experience and recovery from this operation. The pain and MDADI questions will go some way to showing the acceptability of this procedure to patients. It is expected that by 6 weeks the pain and MDADI scores will have returned to near baseline. Most patients will go on to receive radiotherapy to their pharyngeal mucosa, which is known to worsen swallowing function. This data will go some way to clarifying that any subsequent difficulties may not be attributable to the TBM procedure.

Any increased pick up rate resulting from SSS could lead to wider adoption of this process in the management of HNSCCUP. The size of any primary sites identified through SSS over conventional histology will also be recorded and could influence the size of histological levels employed for future TBM and tonsillectomy specimens in the future management of HNSCCUP.

Data from the patient interviews and thematic analysis should help to guide patient goals for any further research in HNSCCUP. Of particular note will be the patients' wishes regarding timing of the tonsillectomy and TBM procedures, which can occur separately, particularly if initial investigation is performed in a peripheral hospital that does not offer TBM. The potential changes in management from identification of primary sites using SSS, and potential for escalation of treatment through the addition of concomitant chemotherapy will also be novel.

Results from the exploratory molecular analysis are expected to give us greater understanding of the molecular make-up of suspected HNSCCUP. Including, but not limited to, how cancers where the primary is identified differ from those primaries that remain occult, and how the cervical disease differs from primary site tissues in the oropharynx.

Results from this prospective observational study will form the foundation of a potential phase III trial investigating the roles of TBM and SSS in management of suspected HNSCCUP. The precise research question is yet to be established.

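### Pain and MDADI change after TBM is summarised without regard to tonsillectomy, so the return to baseline by 6 weeks cannot be credited to TBM alone

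*Protocol*

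**What the plan says.** The second secondary objective is to evaluate swallowing and pain prospectively after TBM. Section 9.3 schedules the questionnaires "at baseline (pre-operatively); and post-operatively at 3 weeks, 6 weeks, 3 months, 6 months, 12 months" and then yearly to 60 months. Section 10.2 describes the first of these as "Baseline Prior to TBM surgery", and the table in Section 10.1 puts it in the Screening/Day 0 column. None of these places mentions tonsillectomy.

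Tonsillectomy is nevertheless part of the work-up for some patients. Section 9.7 asks for "Oropharyngeal tissues from diagnostic surgeries attempting to identify the primary site (i.e., TBM specimens, and tonsils, if available", and Section 12.8 refers to the "timing of the tonsillectomy and TBM procedures, which can occur separately, particularly if initial investigation is performed in a peripheral hospital". The four exclusions in Section 8.3 do not include an earlier tonsillectomy. The nearest is "Primary site identified by any means prior to being indicated for TBM", which leaves in a patient whose tonsillectomy did not find the primary.

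On analysis, Section 12.4 gives means or medians with spread at each time point and adds that "score change between time points will be summarized in the same way". It names a split by surgical method for the pick-up rates and no split for the functional scores. On expectations, Section 12.2 states: "We anticipate no significant change in means from pain and MDADI scores between 0 and 6 week questionnaires". Section 12.8 adds: "It is expected that by 6 weeks the pain and MDADI scores will have returned to near baseline". It then notes that most patients will go on to radiotherapy, which is known to worsen swallowing, and that these data should help to show that later difficulties may have a cause other than TBM.

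**The concern.** To use the 0-to-6-week change as evidence about TBM, two things are needed: a baseline that is not still affected by other recent throat surgery, and a 6-week score that reflects recovery from TBM and not from a second procedure. The protocol's own description of the pathway allows either to fail.

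- **Tonsillectomy shortly before TBM.** The baseline may already carry pain and poorer swallowing. As that resolves, the change score improves, which can offset a worsening caused by TBM.
- **Tonsillectomy at the same operation.** The 3- and 6-week scores may include tonsillectomy recovery, which an undivided table charges to TBM.

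The two effects pull in opposite directions, so the overall mean change depends partly on how many patients had each sequence of surgery. What is at stake is the reading that Section 12.8 gives to this result. The problem arises before radiotherapy starts, so looking at later scores by radiotherapy does not remove it.

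**Working it through.** The protocol gives no standard deviation, margin, sample size or power for pain or MDADI, so there is no planned figure to reproduce. The check sets out the structure of the change score and shows what it does under assumed inputs.

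**Inputs from the protocol**
- Baseline is anchored to TBM only (Sections 9.3, 10.1, 10.2).
- Tonsillectomy may be separate from TBM (Section 12.8) and is not universal (Section 9.7). It is not an exclusion (Section 8.3).
- Change scores are summarised by time point with no split by tonsillectomy (Section 12.4).
- Surgical history and peri-operative outcomes are CRF fields (Section 9.4). The full CRF is not shown.

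**Not given in the protocol:** the share of patients with an earlier or same-session tonsillectomy, the interval from tonsillectomy to TBM, and the size of any residual effect.

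**Formula** (MDADI points, negative = worse)

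Apparent mean change, 0 to 6 weeks = T + fc × C6 − fs × S0

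- T: the change due to TBM alone
- fc: share with tonsillectomy at the same operation
- C6: tonsillectomy effect still present at 6 weeks in those patients
- fs: share with a recent separate tonsillectomy
- S0: tonsillectomy deficit still present at baseline, taken to have resolved by 6 weeks after TBM

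**Illustration.** Every value is assumed; none comes from the protocol. Take T = −5.

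| Case mix | Calculation | Apparent change |
|---|---|---|
| No tonsillectomy effect (fc = fs = 0) | −5 | −5 |
| Half same-session, C6 = −2 | −5 + 0.5 × (−2) | −6.0 |
| Half same-session, C6 = −5 | −5 + 0.5 × (−5) | −7.5 |
| Half recent separate, S0 = −5 | −5 − 0.5 × (−5) | −2.5 |
| Half recent separate, S0 = −10 | −5 − 0.5 × (−10) | 0 |
| Half recent separate, S0 = −15 | −5 − 0.5 × (−15) | +2.5 |
| A quarter of each, C6 = −5, S0 = −5 | −5 − 1.25 + 1.25 | −5.0 |
| A quarter of each, C6 = −2, S0 = −15 | −5 − 0.5 + 3.75 | −1.75 |

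Three things follow.

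1. The same TBM effect can appear larger, smaller, absent or reversed, depending on the mix. In the row with S0 = −10, a 5-point worsening shows as no change, which is the pattern that Section 12.2 anticipates.
2. The bias is fc × C6 − fs × S0. It is zero when the two terms are equal, as in the first quarter-of-each row.
3. If earlier tonsillectomies had fully healed by baseline (S0 = 0), the staged term vanishes whatever the share.

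**The case against.** **The pre-TBM baseline is a reasonable anchor.** The objective is worded as scores after TBM, and patients enter because they are to have TBM. Where tonsillectomy was done earlier elsewhere, a score from before it may predate recruitment. This stands in full. A reader might infer that Section 10.2 sets the wrong baseline; the documents do not support that.

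**The analysis is descriptive and an SAP could add the split.** Section 12.4 does not forbid grouping, and Section 12.8 is cautious: it states an expectation, not a decision rule, and it contrasts TBM mainly with radiotherapy. This stands in part and is why the point is minor. The baseline anchor and the reading placed on it are nevertheless written into the protocol, and Section 12.4 names a split for the pick-up rates but none for these scores.

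**A bias towards apparent recovery might be inferred.** Assuming a staged share of 20% to 50% and a residual deficit of 5 to 15 MDADI points gives 0.20 × 5 = 1.0 to 0.50 × 15 = 7.5 points in that direction. The documents do not support this as an estimate. Both inputs are assumed, the range leaves out zero although healed tonsillectomies would give zero, and it counts only one of two opposing terms.

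**Frequency and timing might be over-read.** Section 12.8 says that separate surgery can occur and where it is more likely, not that it is common. Section 10.2 places baseline before TBM, not immediately before it. Same-session tonsillectomy is implied, not stated.

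**Other surgery could also matter.** Section 9.7 mentions therapeutic neck surgery, so a split by tonsillectomy would not necessarily isolate TBM. This stands as a limit on what the remedy can achieve.

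**Conclusion.** The concern holds as a minor point of interpretation. If Section 12.4 is followed as written, the 0-to-3-week and 0-to-6-week changes may mix recovery from tonsillectomy with recovery from TBM, and a return to near baseline would not by itself support a statement about TBM alone. The size and the net direction of the bias cannot be determined from the protocol; the figures in the illustration show only that the overall mean can move either way. The conclusion rests on two conditions that the protocol allows but does not quantify: that some patients have a tonsillectomy recent enough to affect baseline, or have one at the same operation. If neither occurs in practice, the concern lapses, but an undivided table could not show that.

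**What to change.** - **Section 12.4:** in addition to the overall summaries, report baseline and the changes from baseline to 3 and 6 weeks by tonsillectomy status: none, before TBM (with the interval), and at the same operation.
- **CRF:** confirm that the surgical history and peri-operative fields capture the date of tonsillectomy and whether it was done in the same session as TBM; add these if they do not.
- **Section 12.8:** describe the result as recovery after TBM plus tonsillectomy where both were done. Base any statement about TBM alone on patients without a same-session or recent tonsillectomy, and define recent before the scores are examined.

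The cost is one grouping variable and some extra rows in a descriptive table, with no new visit or questionnaire. The downside is that dividing a planned 100 patients three ways gives smaller groups and less precise means, so the split should be shown beside the overall summary and not in place of it.

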12.1 Sample size

No a prior sample size calculation was performed as initial funding limited recruitment to analysis of 60 specimens to undergo SSS. Meta-analysis shows a pickup rate of 58% for this cohort. We anticipate a potential increase pick up rate of around 10%.

- With 60 specimens, the 95% confidence interval boundaries around the pickup rate are +/- 12.6% for 58% and +/-11.4% for 68%.

In anticipation of further funding, our sample size is increased to 100 to give greater confidence in the effect size.

- With 100 specimens, the 95% confidence interval boundaries around the pickup rate are +/- 9.8% for 58% and +/-9.0% for 68%.

12.2 Study endpoints

For the Primary objective:

- Identification of cancer in the tonsillectomy or TBM specimen on histology.

For the Secondary objectives:

- To compare the pick-up rate of primary cancers in TBM specimens between surgical methods (robotic vs laser vs endoscopic).
 - Identification of cancer in the tonsillectomy or TBM specimen on histology.
 - We anticipate no significant disparity in pick up rate between methods with the limited number of cases in this study.
- To prospectively evaluate swallowing function and pain scores after TBM.
 - We anticipate no significant change in means from pain and MDADI scores between 0 and 6 week questionnaires. Results at 3 weeks are anticipated to be different as still recovering from surgery. Results up to 60 months will evaluate effects of any subsequent treatments and future recovery.
- To understand patient views and experiences of undergoing TBM for suspected HNSCCUP.
 - Qualitative thematic analysis therefore no quantitative end point.
- To report time-to-event data for local, regional and distant disease recurrence, and mortality.
 - Primary emergence rate of around 3% per year.
- To assess the molecular makeup of patients with suspected HNSCCUP undergoing TBM.
 - (Exploratory analysis)

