Human papilloma virus (HPV) is thought to play a significant role in many of these cancers presenting as CUP.[6,7] Smaller or involved primary foci are known to be more common in HPV related cancers which may be contributing to the apparent incidence of these unknown primaries, or occultomas as they may also be called. A histological technique called step serial sectioning (SSS) allows examination of tissue specimens in greater detail than conventional histology. It has not previously been used to investigate the primary site in head and neck cancer but the oropharyngeal tissues that potentially harbour these small primaries make a sensible target to pioneer its usage. It is hypothesised that utilising SSS on tonsillectomy and TBM specimens may increase the identification rate of the primary site and may subsequently affect recommended management.

Currently, we do not understand why some cancers present with cervical metastases with no evident primary site. There has been an explosion in genomics research in many cancers, but this remains an understudied area in head and neck cancer. There are currently no treatments available to patients with head and neck cancer based on genomic insights. This study aims to begin to address the unmet need of patients who present with these poorly understood cancers and to provide a starting point for more detailed investigations into the relationships between cancer genomics and clinical outcomes.

6 Study aim and objectives

6.1 Aim:

To understand the current management of suspected HNSCCUP patients undergoing TBM in the UK, including adequacy of current histology, functional and oncological outcomes, and disease biology.

6.2 Primary objective:

- To establish if step serial sectioning (SSS), compared to conventional histology, improves identification of a primary site in TBM and tonsil specimens in suspected HNSCCUP.

6.3 Secondary objectives:

1. To compare the pick-up rate of primary cancers in TBM specimens between surgical methods (robotic vs laser vs endoscopic).
2. To prospectively evaluate swallowing function and pain scores after TBM.
3. To understand patient views and experiences of undergoing TBM for suspected HNSCCUP.
4. To report time-to-event data for local, regional and distant disease recurrence, and mortality.
5. To assess the molecular makeup of patients with suspected HNSCCUP undergoing TBM.

7 Study design and setting

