9.6 Surgical technique

All centres known to be performing TBM in the UK will be invited to take part. The surgery will take part at the contributing centre adhering to their usual practices. This will encompass techniques using laser resection, endoscopically assisted techniques and resections using robotic systems. There is currently no standardised method for performing TBM. An affiliated project will look to generate a standard operating protocol (SOP) for TBM for potential future studies. The technique used in each case will be recorded on the CRF.

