12.3 Study duration

Recruitment of patients will continue until 100 patients are recruited and undergo TBM. The study duration will be extended as necessary until this target is met across all centres.

The study will remain open until the last patient to be recruited has completed their final 60 month follow-up. Thereafter, end of trial definition will be dependent on resolution of all data queries and completion of database entries in preparation for final statistical analysis and subsequent publication. Once these stages have been reached and the study paperwork is ready for archiving, a 'Declaration of End of Study Form' will be sent to RMH R&D and to the Research Ethics Committee (Health Research Authority) notifying them that the study is now concluded. A summary of the final research report will be provided to the Committee within 12 months of the conclusion of the study. This will report on whether the study achieved its objectives, summarise the main findings, and confirm arrangements for publication or dissemination of the research including any feedback to participants.

Summary of project timings (correct at time of drafting v2.2)

Date	Activity
Dec 2018	First draft of protocol
Jan 2019	Protocol submission to sponsor (CCR)
Feb 2019	CCR review
May 2019	Submission via IRAS
July 2019	REC/HRA approvals
Nov 2019	Opening of first sites
March 2020	COVID-19 disruption
October 2023	Completion of recruitment
October 2028	Completion of 60 month follow up for all patients

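### The endpoint listed for the surgical-method comparison also counts tonsil cancers, although the objective concerns TBM specimens only

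*Protocol*

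**What the plan says.** The objective appears in the same words in the project summary (section 3), in section 6.3 and in section 12.2: "To compare the pick-up rate of primary cancers in TBM specimens between surgical methods (robotic vs laser vs endoscopic". It names TBM specimens and no other tissue. The endpoint listed directly beneath it in section 12.2 is "Identification of cancer in the tonsillectomy or TBM specimen on histology", identical to the endpoint given for the primary objective.

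Section 12.4 says that conventional histology (CH) and step serial sectioning (SSS) pick-up will be "reported in the overall specimens and separately in the sub-group of surgical methods with 95% confidence intervals". It does not say which specimens enter the sub-groups.

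Three other sections matter here:

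- Section 9.6 lists laser, endoscopically assisted and robotic surgery as ways of performing TBM, and adds "The technique used in each case will be recorded on the CRF".
- Section 9.7 requests "Oropharyngeal tissues from diagnostic surgeries attempting to identify the primary site (i.e., TBM specimens, and tonsils, if available", so one case may supply both kinds of tissue.
- Section 12.8 notes that tonsillectomy and TBM may be done at different times.

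**The concern.** The combined endpoint suits the primary objective, which covers both TBM and tonsil specimens. It does not suit an objective about TBM specimens by TBM technique. If technique is a label on the case and the case is positive when either tissue is positive, a tonsil-only cancer is credited to the TBM technique although the TBM specimen was negative.

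Two techniques with equal tongue-base yield could then appear to differ because tonsil tissue was available more often, or was positive more often, with one of them. A real difference in tongue-base yield could also be diluted. Section 12.8 expects the results to support a possible phase III trial on the role of TBM, so a yield reported by technique should mean what its label says.

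**Working it through.** **Text comparison**

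| Item | Tissue named |
|---|---|
| Primary objective (6.2) | TBM and tonsil |
| Primary endpoint (12.2) | tonsil or TBM |
| Secondary objective 1 (3, 6.3, 12.2) | TBM only |
| Endpoint under secondary objective 1 (12.2) | tonsil or TBM |
| Analysis by method (12.4) | not restricted |

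The first pair agrees and the second does not. The exclusion in section 8.3, "Primary site identified by any means prior to being indicated for TBM", removes primaries known before TBM was indicated. It does not remove tonsil cancers found at the same operation or only later on SSS.

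**Illustration**

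The protocol gives no pick-up figure by method, so there is nothing to reproduce. It also gives no tonsil availability, tonsil yield or TBM-only yield. All inputs below are therefore assumptions: TBM yield p = 0.45 for both methods, tonsil yield y, and share of cases with tonsil tissue a.

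- Per patient, findings independent: rate = p + (1 - p) × a × y
- Pooled per specimen, one tonsil specimen per case that has any: rate = (p + a × y) / (1 + a)

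Base case, y = 0.20, a = 0.80 versus 0.20:

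- Per patient: 0.45 + 0.55 × 0.16 = 0.538 versus 0.45 + 0.55 × 0.04 = 0.472; gap +6.6 points.
- Per specimen: 0.61/1.8 = 0.339 versus 0.49/1.2 = 0.408; gap -6.9 points.

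| Assumptions | Gap per patient | Gap per specimen |
|---|---|---|
| y = 0.20, a = 0.80 vs 0.20 | +6.6 | -6.9 |
| y = 0.20, a = 0.60 vs 0.40 | +2.2 | -2.2 |
| y = 0.30, a = 0.80 vs 0.20 | +9.9 | -4.2 |
| y = 0.10, a = 0.80 vs 0.20 | +3.3 | -9.7 |
| y = 0.20, a = 0.50 in both | 0 | 0 |

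In the last row the gap is nil, but the reported rate is 0.45 + 0.55 × 0.10 = 50.5% per patient or 0.55/1.5 = 36.7% per specimen, against a TBM rate of 45%. With these values a true TBM difference between methods would also be multiplied by 1 - a × y = 0.90 per patient, or 1/(1 + a) = 0.67 per specimen.

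The sign depends on the unit of analysis, which the protocol does not settle. Section 12.1 counts specimens ("With 100 specimens, the 95% confidence interval boundaries around the pickup rate are") and section 12.3 counts patients ("Recruitment of patients will continue until 100 patients are recruited and undergo TBM").

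**Sampling error in the base case**, assuming 33 patients per method:

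- Per patient: 1.96 × √(0.538 × 0.462/33 + 0.472 × 0.528/33) = 0.241, about 24 points.
- Per specimen, with 33 × 1.8 = 59.4 and 33 × 1.2 = 39.6 specimens: 1.96 × √(0.339 × 0.661/59.4 + 0.408 × 0.592/39.6) = 0.195, about 19 points, ignoring clustering within patients.

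The illustration does not separate CH from SSS and does not model the exclusion in section 8.3.

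**The case against.** The best defence is that the TBM restriction is stated three times, the last time as the line under which the endpoint sits. A sensible analyst might read the endpoint as a pasted definition of a positive finding, to be applied within TBM specimens. Section 12.4 is silent rather than wrong, and an SAP could supply the restriction. That reading is possible, but it goes against the endpoint's own words, which include the tonsillectomy specimen. An SAP that followed the protocol's endpoint would carry the mismatch forward.

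Other points stand in part:

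- The two rates can coincide: per patient if there are no tonsil-only cancers, per specimen if tonsil and TBM yields are equal. That would be a coincidence of values and would not make the endpoint the right one.
- The protocol does not say how tonsillectomies are performed, so the same approach may sometimes be used for both tissues. A tonsil cancer is still not a finding in the TBM specimen.
- The 80% versus 20% contrast has no basis in the documents, and section 8.3 removes cancers found at an earlier tonsillectomy. The illustration shows a mechanism and does not estimate an effect.
- The analysis is descriptive, and section 12.2 itself expects no significant disparity with so few cases. This limits the weight of the point.
- The question of specimens or patients as the unit is wider than this objective. It is used here only to show that even the direction of the distortion is open.

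**Conclusion.** The concern holds: the endpoint in section 12.2 contradicts the objective it serves, and nothing else in the protocol restores the restriction to TBM specimens. This conclusion rests on the text alone.

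The numerical consequence cannot be derived from the documents. Under the assumptions shown, two methods with the same TBM yield differ by 2.2 to 9.9 points in absolute value when tonsil availability differs, with opposite signs for the two units of analysis. The base-case gaps are well inside the sampling error expected with 33 patients per method. With equal tonsil availability and yield there is no spurious gap, but the quantity reported is still not TBM pick-up. The mismatch touches one descriptive secondary objective; the combined endpoint remains right for the primary objective. It should be corrected, but it does not threaten the study's main result.

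**What to change.** In section 12.2, under secondary objective 1, define the endpoint as cancer identified on histology in the TBM specimen. In section 12.4, state that CH and SSS pick-up by surgical method is reported in TBM specimens only, with numerator and denominator for each method. Keep the combined tonsil-or-TBM endpoint for the primary objective.

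The sponsor should also confirm that TBM and tonsil results can be told apart. Section 9.4 lists the conventional and SSS histology results without saying whether they are recorded by tissue. If they are not, the split would have to come from the local histopathology reports and the SSS pathologist's report, both provided for in section 9.7.

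The cost is one line and one phrase, plus that check. Technique is already recorded for each case, and no visit, sample or treatment changes. The downside is slightly fewer positive findings in each method sub-group.
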